4.2.5 Resumption of Treatment after Dose Delay

If there is a delay in treatment due to AEs associated with study medication, when the patient resumes treatment, he/she will receive the next dose, rather than the missed dose. If the dose delay occurs during the combination treatment (induction), the patient will receive less than 4 doses of the combination treatment.

If there is a delay due to SRT or AEs not associated with study medication, when the patient resumes treatment, he/she will receive the missed dose. If the dose delay occurs during the combination treatment (induction), the patient has the opportunity to receive all four doses of the combination treatment.

4.3 CONCOMITANT AND EXCLUDED THERAPIES

Medications or vaccinations specifically prohibited in the exclusion criteria are not allowed during the ongoing trial. If there is a clinical indication for any medication or vaccination specifically prohibited during the trial, discontinuation from trial therapy or vaccination may be required. The final decision on any supportive therapy or vaccination rests with the investigator and/or the subject's primary physician. However, the decision to continue the subject on trial therapy or vaccination schedule requires the mutual agreement of the investigator, and the subject.

4.3.1 Acceptable Concomitant Medications

All treatments that the Investigator considers necessary for a subject's welfare may be administered at the discretion of the Investigator in keeping with the community standards of medical care. All concomitant medication will be recorded on the eCRF including all prescription, over-the-counter (OTC) products, herbal supplements, and IV medications and fluids. If changes occur during the trial period, documentation of drug dosage, frequency, route, and date should also be included on the eCRF.

All concomitant medications received within 28 days prior to the screening visit and up to 30 days after the last dose of trial treatment should be recorded. Concomitant medications administered 30 days after the last dose of trial treatment should be recorded for SAEs and ECIs.

4.3.1.1 Permitted Therapies: SRT and palliative radiation to NON-CNS lesions

If a subject demonstrates clinical benefit, but disease progression in ≤ 5 brain metastases occurs, the investigator may prescribe SRT (single episode), and two scenarios are permitted as detailed below.

- If the patient is clinically stable, progression should be confirmed by follow-up imaging after 4 weeks. If progression is confirmed, the patient may undergo SRT treatment (single episode) for ≤ 5 lesions and may receive ≤ 16 mg dexamethasone PO daily tapered in ≤ 4 weeks. Treatment with the study drugs can be resumed after taper completion as long as the patient does not demonstrate criteria for discontinuation (see Section 4.2.2).
- If the patient is symptomatic as a result of the disease progression, and clinical assessment indicates a requirement for SRT without the delay imposed by the 4-week confirmatory scan, the patient may undergo SRT and may receive ≤ 16 mg dexamethasone PO daily tapered in ≤ 4 weeks. Treatment with the study drugs can be resumed after the completion of the taper as long as the patient does not demonstrate criteria for discontinuation (see Section 4.2.2).

Proprietary Information of MD Anderson

NOTE: To continue on study after SRT, at least 1 non-irradiated target lesion must remain after SRT treatment.

Recommended Observation Period after On-Study SRT

Subjects should be evaluated for neurologic toxicity during the post-SRT treatment window as defined below:

- Subjects receiving SRT during induction (pembrolizumab combined with ipilimumab every 3 weeks for up to 4 doses) should be followed for 3 weeks following the next pembrolizumab with ipilimumab dose. The resumption of treatment with study drugs after SRT is specified in Section 4.2.3 and Section 4.2.4.
- Subjects receiving SRT during maintenance (pembrolizumab every 3 weeks) should be followed for a period of 2 weeks following the next dose. The resumption of treatment with study drugs after SRT is specified in Section 4.2.3 and Section 4.2.4.

Criteria for discontinuation can be found in Section 4.2.2.

For patients who require palliative radiation to NON-CNS lesions: this can be performed while receiving treatment with immunotherapy, and treatment does not need to be held.

4.3.1.2 Permitted Therapy for Brain Edema

Steroid treatment \leq 16 mg dexamethasone PO daily tapered in \leq 4 weeks is allowed only for the treatment of brain edema (single episode). If a second episode of brain edema requires steroid treatment, the overall study primary investigator must be consulted.

4.3.1.3 Permitted Therapy: Brain Surgery

If a subject has disease progression in the brain and qualifies as a medical emergency, a single surgical intervention is permitted with the approval of the PI. To remain on-study, the subject must have remaining measurable disease in the brain.

4.3.2 Prohibited Concomitant Medications

Subjects are prohibited from receiving the following therapies during the Screening and Treatment Phase (including Second Course Phase) of this trial:

- Immunosuppressive agents
- Immunosuppressive doses of systemic corticosteroids

Note: Inhaled or topical steroids, and adrenal replacement steroid doses $>$ 10 mg daily prednisone equivalent, are permitted in the absence of active autoimmune disease.

- Antineoplastic systemic chemotherapy or biological therapy
- Immunotherapy not specified in this protocol
- Chemotherapy not specified in this protocol
- Investigational agents other than pembrolizumab or ipilimumab

- Live vaccines within 30 days prior to the first dose of trial treatment and while participating in the trial. Examples of live vaccines include, but are not limited to, the following: measles, mumps, rubella, varicella/zoster, yellow fever, rabies, BCG, and typhoid vaccine. Seasonal influenza vaccines for injection are generally killed virus vaccines and are allowed; however, intranasal influenza vaccines (e.g., FluMist®) are live attenuated vaccines and

Low-Dose Ipilimumab with Pembrolizumab – University of Texas MD Anderson Cancer Center

2018-0875, Version 1.6

Proprietary Information of MD Anderson

are not allowed.

- Systemic glucocorticoids for any purpose other than to modulate symptoms from a drug-related AE of suspected immunologic etiology. Please note that inhaled or topical steroids are allowed, and systemic steroids at doses \leq 10 mg/day prednisone or equivalent are allowed, as described in Section 5.6.
- Local surgery resulting from disease progression is prohibited. However, if indicated for palliative measure and after Sponsor approval, local surgery may be permitted beyond Week 12 tumor assessment.

Subjects who, in the assessment of the Investigator, require the use of any of the aforementioned treatments for clinical management should be removed from the trial. Subjects may receive other medications that the Investigator deems to be medically necessary.

The Exclusion Criteria describes other medications, which are prohibited in this trial.

There are no prohibited therapies during the Post-Treatment follow-up Phase.

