4.2.2.1 Pembrolizumab Dose Modifications

See the table below for Dose Modification guidelines for pembrolizumab.

Table 3: Dose modification and toxicity management guidelines for immune-related AEs associated with pembrolizumab monotherapy and IO Combinations

General instructions:
 
 1. Severe and life-threatening irAEs should be treated with IV corticosteroids followed by oral steroids. Other immunosuppressive treatment should begin if the irAEs are not controlled by corticosteroids. 2. Study intervention must be permanently discontinued if the irAE does not resolve or the corticosteroid dose is not \leq10 mg/day within 12 weeks of the last study intervention treatment. 3. The corticosteroid taper should begin when the irAE is \leq Grade 1 and continue at least 4 weeks. 4. If study intervention has been withheld, study intervention may resume after the irAE decreased to \leq Grade 1 after corticosteroid taper. 				
--	--	--	--	--

irAEs	Toxicity Grade (CTCAE v5.0)	Action With Pembrolizumab	Corticosteroid and/or Other Therapies	Monitoring and Follow-up
Pneumonitis	Grade 2	Withhold	
 • Administer corticosteroids (initial dose of 1 to 2 mg/kg prednisone or equivalent) followed by taper 	
 • Monitor participants for signs and symptoms of pneumonitis
	Recurrent Grade 2, Grade 3 or 4	Permanently discontinue	
 • Add prophylactic antibiotics for opportunistic infections 	
 • Evaluate participants with suspected pneumonitis with radiographic imaging and initiate corticosteroid treatment
Diarrhea/Colitis	Grade 2 or 3	Withhold	
 • Administer corticosteroids (initial dose of 1 to 2 mg/kg prednisone or equivalent) followed by taper 	
 • Monitor participants for signs and symptoms of enterocolitis (ie, diarrhea, abdominal pain, blood or mucus in stool with or without fever) and of bowel perforation (ie, peritoneal signs and ileus)
	Recurrent Grade 3 or Grade 4	Permanently discontinue		
 • Participants with \geqGrade 2 diarrhea suspecting colitis should consider GI consultation and performing endoscopy to rule out colitis

irAEs	Toxicity Grade (CTCAE v5.0)	Action With Pembrolizumab	Corticosteroid and/or Other Therapies	Monitoring and Follow-up

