If the toxicities do resolve and conditions are aligned with what is define then treatment may be restarted at the discretion of the investigator.[In these cases where the toxicity is attributed to Pembro or the combination, re-initiation of pembrolizumab as a monotherapy may be considered at the principal investigator's discretion.

Table 4: Pembrolizumab Infusion Reaction Dose modification and Treatment Guidelines

NCI CTCAE Grade	Treatment	Premedication at Subsequent Dosing
Grade 1 Mild reaction; infusion interruption not indicated; intervention not indicated	Increase monitoring of vital signs as medically indicated until the participant is deemed medically stable in the opinion of the investigator.	None
Grade 2 Requires therapy or infusion interruption but responds promptly to symptomatic treatment (e.g., antihistamines, NSAIDs, narcotics, IV fluids); prophylactic medications indicated for ≤24 hrs	
Stop Infusion.
 
Additional appropriate medical therapy may include but is not limited to:
 
IV fluids Antihistamines NSAIDs Acetaminophen Narcotics
 
Increase monitoring of vital signs as medically indicated until the participant is deemed medically stable in the opinion of the investigator.
 
If symptoms resolve within 1 hour of stopping drug infusion, the infusion may be restarted at 50% of the
	
Participant may be pre-medicated 1.5h (\pm 30 minutes) prior to infusion of pembrolizumab with:
 
Diphenhydramine 50 mg po (or equivalent dose of antihistamine).
 
Acetaminophen 500-1000 mg po (or equivalent dose of analgesic).

	
original infusion rate (e.g. from 100 mL/hr to 50 mL/hr). Otherwise dosing will be held until symptoms resolve and the participant should be premedicated for the next scheduled dose.
 
Participants who develop Grade 2 toxicity despite adequate premedication should be permanently discontinued from further study drug treatment
	

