4.5 SUPPORTIVE CARE GUIDELINES

Subjects should receive appropriate supportive care measures as deemed necessary by the treating investigator. Suggested supportive care measures for the management of adverse events with potential immunologic etiology are outlined below. Where appropriate, these guidelines include

Low-Dose Ipilimumab with Pembrolizumab – University of Texas MD Anderson Cancer Center

2018-0875, Version 1.6

Proprietary Information of MD Anderson

the use of oral or intravenous treatment with corticosteroids as well as additional anti-inflammatory agents if symptoms do not improve with administration of corticosteroids. Note that several courses of steroid tapering may be necessary as symptoms may worsen when the steroid dose is decreased. For each disorder, attempts should be made to rule out other causes such as metastatic disease or bacterial or viral infection, which might require additional supportive care. The treatment guidelines are intended to be applied when the investigator determines the events to be related to pembrolizumab.

Note: if after the evaluation the event is determined not to be related, the investigator does not need to follow the treatment guidance (as outlined below). Refer to Section 8.0 for dose modification.

It may be necessary to perform conditional procedures such as bronchoscopy, endoscopy, or skin photography as part of evaluation of the event.

- **Pneumonitis:**

- For **Grade 2 events**, treat with systemic corticosteroids. When symptoms improve to Grade 1 or less, steroid taper should be started and continued over no less than 4 weeks.
- For **Grade 3-4 events**, immediately treat with intravenous steroids. Administer additional anti-inflammatory measures, as needed.
- Add prophylactic antibiotics for opportunistic infections in the case of prolonged steroid administration.

- **Diarrhea/Colitis:**

Subjects should be carefully monitored for signs and symptoms of enterocolitis (such as diarrhea, abdominal pain, blood or mucus in stool, with or without fever) and of bowel perforation (such as peritoneal signs and ileus).

- All subjects who experience diarrhea/colitis should be advised to drink liberal quantities of clear fluids. If sufficient oral fluid intake is not feasible, fluid and electrolytes should be substituted via IV infusion. For Grade 2 or higher diarrhea, consider GI consultation and endoscopy to confirm or rule out colitis.

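### Section 4.3.2 bans immunosuppressive agents and removes patients who need them, while Table 3 directs such agents for steroid-refractory immune toxicity and lets study treatment resume

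*Combined protocol and SAP*

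**What the plan says.** **The prohibition.** Section 4.3.2 opens with "Subjects are prohibited from receiving the following therapies during the Screening and Treatment Phase", and it extends this to the second course. Immunosuppressive agents are the first item on the list. The second is immunosuppressive doses of systemic corticosteroids. A note below them covers only inhaled, topical and adrenal-replacement steroids. A later item restricts systemic glucocorticoids but exempts their use for drug-related events of suspected immune origin. The closing rule is that subjects who, in the investigator's assessment, "require the use of any of the aforementioned treatments for clinical management should be removed from the trial".

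**The irAE instructions.** The general instructions to Table 3 (Section 4.2.2.1) say: "Other immunosuppressive treatment should begin if the irAEs are not controlled by corticosteroids". They continue: "If study intervention has been withheld, study intervention may resume after the irAE decreased to" Grade 1 or lower after the steroid taper. The limit is also stated: "Study intervention must be permanently discontinued if the irAE does not resolve or the corticosteroid dose is not" down to 10 mg/day within 12 weeks of the last study treatment. The text between Tables 3 and 4 adds that, once toxicity has resolved and the conditions are met, "treatment may be restarted at the discretion of the investigator".

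**Related text.** Section 4.5 suggests, where appropriate, "additional anti-inflammatory agents if symptoms do not improve with administration of corticosteroids", and for Grade 3-4 pneumonitis it says "Administer additional anti-inflammatory measures, as needed". Section 4.3 says that a clinical need for a prohibited medication may lead to discontinuation from trial therapy, and it makes continuation a joint decision of investigator and subject. Section 3 says that subjects discontinued from treatment continue to be followed for safety, progression and overall survival (OS). Section 4.6.4 makes follow-up after stopping study drug mandatory.

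**The concern.** A site that follows Table 3 for an irAE not controlled by steroids gives a therapy from the Section 4.3.2 prohibited list. Table 3 may then allow that patient to restart, whereas Section 4.3.2 calls for removal. The triggering event is expected toxicity of the study combination, and the treatment is one the protocol itself directs.

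Two things are at stake. The first is consistent handling of toxicity: like patients may be treated differently, and a site following the protocol's own toxicity table is also using a prohibited therapy. The second is endpoint follow-up. The primary endpoint (Sections 2.1 and 6.1) counts complete response, partial response, or stable disease beyond 6 months in the brain. A patient with stable disease needs brain imaging past that point to be classified. Section 4.3.2 says removal from the trial rather than from study drug. Read literally, that ends assessment for a reason related to toxicity, and Section 6.2.1 does not say how such a patient is counted.

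**Working it through.** No figure in the plan depends on this point, so the check is a comparison of the passages.

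**Step 1: does the prohibition reach the treatment Table 3 directs?** Table 3 refers to immunosuppression other than corticosteroids. Section 4.3.2 lists immunosuppressive agents without qualification. Its exceptions cover steroids only: the note on inhaled, topical and replacement steroids, and the glucocorticoid item with its immune-event exemption. None reaches a non-steroid agent. The permission at the end of Section 4.3.2 to give other necessary medications applies to drugs not on the list.

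**Step 2: which patients face contradictory instructions?**

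| Situation | Table 3 and the text after it | Section 4.3.2 | Section 4.3 |
|---|---|---|---|
| Steroid-refractory irAE, withhold row, conditions for restart met | Give other immunosuppression; study treatment may resume | Remove from the trial | Discontinuation from trial therapy possible, not required |
| Steroid-refractory irAE, permanent-discontinuation row | Give other immunosuppression; no restart | Remove from the trial | As above |
| irAE controlled by steroids alone | Steroids; restart rules apply | Exempted by the later glucocorticoid item | Not engaged |

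The restart conflict lies in the first row. Withhold entries include Grade 2 pneumonitis, Grade 2 or 3 diarrhea/colitis, Grade 2 liver enzyme or bilirubin elevation, and Grade 2 nephritis. In the second row study drug stops either way, but the protocol still both directs and prohibits the agent, and it is still unclear whether follow-up ends. The third row needs only a cross-reference: the item on immunosuppressive steroid doses has no irAE exception of its own, but the later item in the same list supplies one.

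**Step 3: does removal agree with the follow-up rules?**

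- Section 3 continues follow-up for safety, progression and OS in all subjects discontinued from treatment. For those who stop for reasons other than progression, it follows disease status until progression, non-study cancer treatment, withdrawal of consent or loss to follow-up.
- Section 4.6.4 requires follow-up until death or the end of the study.
- Footnote f of the Section 5 schedule runs MRI until progression or discontinuation of treatment, whichever is later, with follow-up scans ordered as standard of care.
- Section 4.3.2 itself mentions a post-treatment follow-up phase with no prohibited therapies.

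These provisions assume that stopping study drug is not leaving the trial. The removal sentence does not make that distinction.

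**Step 4: size.** Cohort A has 25 subjects (Section 3), so each patient whose benefit status changes moves the CBR by 1/25 = 0.04, or 4 percentage points. The documents give no rate of steroid-refractory irAEs or of second-agent use, so the expected number of patients cannot be calculated.

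**The case against.** The strongest reply is that other text softens the rule. Section 4.3 leaves supportive therapy to the investigator or primary physician and makes discontinuation only possible. Section 4.3.1 allows treatments needed for the subject's welfare. These provisions show discretion was intended, but they neither exempt non-steroid agents nor cancel the removal sentence. They are further text to reconcile.

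A second reply is that Section 4.5 only suggests anti-inflammatory agents and contains no restart rule. That is correct, so Section 4.5 is supporting evidence only. Table 3 and the text after it establish the conflict without it.

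Three stronger readings are tempting, and the documents do not support them.

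- *Steroids for irAEs are banned outright.* The glucocorticoid exemption in the same list largely covers them. What remains is a wording point.
- *These patients are lost before the primary endpoint can be observed, or leave the CBR denominator.* Sections 3 and 4.6.4 and footnote f of the schedule keep them in follow-up. A response already recorded is not erased, and nothing excludes them from the denominator. The defect is that the removal sentence contradicts those provisions.
- *Power falls by a calculable amount.* That needs a removal rate, and none is given. The 45% Grade 3-4 figure in Section 1.2 covers all such toxicity in KEYNOTE-029, which gave pembrolizumab 2 mg/kg rather than the 200 mg used here and excluded patients with brain metastases. It is not a rate of steroid-refractory events.

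**Conclusion.** The contradiction is in the current text and rests on no outside source or assumed figure. For a patient with a steroid-refractory irAE in a withhold row, Table 3 directs an agent that Section 4.3.2 prohibits, and the two sections then give incompatible consequences: possible restart or removal. Section 4.3 gives a third, softer rule. Separately, removal from the trial is at odds with Sections 3 and 4.6.4.

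The affected group is narrow. Restart requires recovery to Grade 1 or lower after taper, compliance with the 12-week limit, and a row that does not require permanent discontinuation. Its frequency is unknown, so the only size the documents support is 4 percentage points of CBR for each Cohort A patient whose classification changes. The point should be corrected because it affects toxicity handling and endpoint follow-up and is cheap to settle. It does not show that the design or sample size is wrong.

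**What to change.** 1. Reconcile Section 4.3.2 with Table 3, the restart text after it, and Section 4.3. State in the immunosuppressive-agents item whether non-steroid treatment of an irAE given under Table 3 falls under the prohibition, and use the same rule in all four places. Which clinical rule applies is for the sponsor and investigator.
2. Reword the removal sentence so that stopping study drug is separate from stopping follow-up, in line with Sections 3 and 4.6.4. Say that these patients keep their disease assessments, including brain imaging, and add to Section 6.2.1 that they stay in the CBR denominator.
3. Add a cross-reference from the item on immunosuppressive steroid doses to the glucocorticoid exemption later in the list.

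The cost is a short protocol amendment with the IRB approval that Section 8.3 requires for any modification. It adds no procedures, visits or patients.

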4.4 STUDY ASSESSMENTS

4.4.1 Adverse Event (AE) Monitoring

The Investigator or qualified designee will assess each subject to evaluate for potential new or worsening AEs as specified in the Trial Flow Chart (Section 6) and more frequently if clinically indicated. Adverse events will be graded and recorded throughout the trial and during the follow-up period according to NCI CTCAE Version 4.03 (see [Section 12.5]). Toxicities will be characterized in terms including seriousness, causality, toxicity grading, and action taken with regard to trial treatment.

All AEs of unknown etiology associated with pembrolizumab or ipilimumab exposure should be evaluated to determine if it is possibly an event of clinical interest (ECI) of a potentially immunologic etiology (irAE). See Section 5.6.1 and the separate guidance document in the administrative binder regarding the identification, evaluation and management of AEs of a potential immunological etiology.

Please refer to Section 7.1 for detailed information regarding the assessment and recording of AEs.

